### **Use of wearable sensors and self-report of symptoms among psychiatric patients**

In a systematic review of 35 studies that use data collected from the mobile phone and information collected through wearable sensors, Seppälä et al. (2019) found an association between data collected by sensors and symptoms of schizophrenia, bipolar disorders, and

depression. However, the use of such data in clinical settings to support therapeutic interventions is not yet been thoroughly evaluated.

Lahti and his associates (2021) found that there is a possibility to identify an association between data collected by sensors, to the worsening of the mental state of patients diagnosed with schizophrenia. These illustrate the need for further research in the unique population of psychiatric patients and the lack of research information concerning hospitalized psychiatric patients during the acute phase of their illness.

Zarbo and colleagues (2022) assessed adherence to and usability of the Experience Sampling Method (ESM) and actigraph in patients with a schizophrenia spectrum disorder. They found differences in compliance between the patients residing in psychiatric rehabilitation housing in the community and healthy controls. They reported that the presence of a multi-disciplinary team is critical to ensure patients' responsiveness to using wearable sensors and answering ESM questionnaires. A complete psychiatric hospitalization setting constitutes an environment adapted to patients' compliance for monitoring. Zarbo et al. (2022) also pointed out that subjects monitored through ESM questionnaires and actigraphs reported that their involvement in the monitoring process improved their mental well-being through understanding their feelings, attention to daily routines, and rewarding occupation in utilizing their time. Participation in the monitoring procedure affects the patient's experience; this function deserves further research.

## Research Objectives

### 1. General purpose

The present study aims to develop an Experience Sampling Method (ESM) questionnaire tailored specifically for the distinctive context of psychiatric hospitalization; an instrument not currently employed in the clinical field. The study will outline the various stages involved in questionnaire development. The primary objective of this study is to validate the ESM questionnaire by comparing the trends in symptom severity as reported through the ESM questionnaire with the PANSS assessment of symptom severity during a 14-day psychiatric hospitalization period.

### 2. Specific Aims:

1. Development of an ESM questionnaire specifically tailored to the unique circumstances psychiatric patients face during their hospitalization.

2. Investigation of the feasibility and compliance of patients in participating in the study, including their willingness to complete digital ESM questionnaires three times a day and wear the smartwatch sensor throughout their hospitalization. Additionally, we will explore potential differences in adherence and compliance among subjects with different psychiatric diagnoses regarding their willingness to participate in the study, complete self-report ESM questionnaires, and wear the smartwatch.
3. Examination of the validity of the ESM questionnaire in predicting the trends of change in symptom severity among psychiatric patients during a 14-day psychiatric hospitalization period. This validity will be evaluated by comparing the trends in symptom severity as measured by the ESM questionnaire with the trends observed in four PANSS assessments conducted throughout the hospitalization.
4. The validity of subjects' self-reports on sleep quality and activity level will be assessed by comparing the self-report ESM data with the physiological indicators collected by the smartwatch. Additionally, the ESM indices will be compared to reports from the nursing staff on the ward. Furthermore, we will explore whether these comparisons yield different outcomes among subjects with different psychiatric diagnoses.
5. The effectiveness of the monitoring model will be assessed by examining the impact of exposing the psychiatrists to ESM data, as well as the physiological indicators collected by the smartwatch, on the decision-making process regarding changes in the patient's medication plan during psychiatric hospitalization.
6. Patient satisfaction:

Assessing patient satisfaction with the monitoring model used throughout their 14-day hospitalization. Following the monitoring period, subjects will be asked to provide feedback on their satisfaction levels through questionnaires.

7. The satisfaction of the multi-disciplinary teams (physicians, nursing staff, clinical psychologists, social workers, occupational therapists):

At the end of the study, the teams will report through questionnaires on their satisfaction with using this monitoring model and its influence on the team's clinical decision-making.

## Description of the research process

The research will be carried out in two phases:

1. **Development of the monitoring questionnaire - Content validity phase** - This phase has been fully completed, and its results will be presented in the preliminary

results chapter. At this research stage, the core content domains of the monitoring questionnaire will be developed. The research process in this phase includes the following:

1. Examining the content of scales from the Positive and Negative Syndrome Scale (PANSS) for schizophrenia and The Symptom Checklist-90-R (SCL-90-R) questionnaire: At this stage, the psychiatric symptoms, and the main criteria for assessing a mental state as emerged from those questionnaires were examined for discussion in the focus groups.
2. Focus group No. 1: The first focus group included patients hospitalized in the psychiatric ward. The purpose of the focus group is to formulate the ESM core and additional content domains and the questionnaire items and to discuss the optimal measurement frequency according to the hospitalized patients' opinions. The focus group will also examine the wording that best suits how the patients describe their mental state.

## **Participants**

The focus group recruited nine subjects over age 18 (6 women and three men) hospitalized by consent in the psychiatric wards at the Sheba Medical Center, who signed informed consent to participate in the study. The criteria for exclusion from the study were: patients with a low level of compliance to treatment, patients suffering from a significant active physical illness, intellectual disability, or complex organic conditions including dementia conditions, patients who cannot read and write in the Hebrew language, patients who are not qualified to give informed consent. The participants were given a refund of expenses for canceling the time involved in participating in the focus group using shopping vouchers of 100 NIS.

## **Indices**

The subjects' point of view regarding the psychiatric symptoms they suffered from during their hospitalization was examined during a free discussion. Emphasis was placed on the symptoms that change daily throughout the hospitalization and how much they indicate a change in their mental state. We also investigated what information they would like to report to the treatment team about their mental state throughout the hospitalization. After the free discussion, the position of the

subjects was examined regarding the criteria for assessing mental state as they emerged from the monitoring scales of the PROM questionnaires.

After a qualitative analysis of the information collected at this stage, the main themes of the ESM questionnaire were formulated. According to the themes found, suggestions were developed for the questionnaire items while noting how the patient's symptoms were worded. A professional transcriber transcribed the discussion.

3. Focus group No. 2: The second focus group includes a multi-disciplinary team working in the psychiatric inpatient wards. In a free discussion, the multi-disciplinary team members examined the core issues that should appear in the questionnaire for monitoring the mental state of hospitalized patients, then explored and expressed their opinion regarding the issues raised by the patients in the first focus group. The result of this step will be an ESM questionnaire adapted to the needs of the patients and the clinical staff in the inpatient wards.

## **Participants**

At this stage, seven staff members working in the psychiatric hospitalization wards in Sheba Medical Center (3 women and four men), who signed informed consent to participate in the study, participated in the focus group. Inclusion criteria: Staff members work in the inpatient wards and have a valid Israeli license. The group was attended by two physicians in the psychiatry internship stage, two nursing staff members, an occupational therapist, a social worker, and a clinical psychologist.

## **Indices**

In the discussion, the participants floated important themes for monitoring according to their points of view. After a free discussion, the participants were presented with the themes raised by the patients in the previous focus group. They were also presented with the possible questionnaire items formulated after the last stage, and their position was examined regarding the appropriateness of fitting these items to the questionnaire. In addition, the discussion dealt with the optimal sampling frequency, in their opinion.

## **The initial formulation of the ESM questionnaire items.**

The questionnaire items were formulated considering the information collected in the focus groups. An effort was made to use the patients' words to ask about their mental state. In addition, existing and valid self-report items marked as necessary by the patients and staff in the focus groups discussion were selected. Items from these questionnaires were reformulated according to the ESM approach that examines the current state. At the end of this stage, an ESM questionnaire was developed, which consists of 15 items on a five levels Likert scale. In the questionnaire, there was another item of a Visual Analogue Scale type where the subject had to mark his mood on a scale ranging from 1-100.

4. Focus group No.3: The third focus group included hospitalized inpatients for cognitive debriefing - Cognitive debriefing is the process by which a patient questionnaire is actively tested among representatives of the target population and target language group to determine whether respondents understand the questionnaire as the authors intended it to be understood.

### **Participants**

The focus group recruited six subjects over 18 (two women and four men) hospitalized with consent in the psychiatric unit at the Sheba Medical Center, who signed an informed consent to participate in the study. The criteria for exclusion from the study were: patients with a low level of compliance to treatment, patients suffering from a significant active physical illness, developmental, intellectual disability, or complex organic conditions including dementia, patients who cannot read and write in the Hebrew language, patients who are not qualified to give informed consent. The participants were given a refund of expenses for canceling the time involved in participating in the focus group using shopping vouchers of 100 NIS.

### **Indices**

For each item in the developed ESM questionnaire, subjects were asked to describe freely what they thought the item was testing. In addition, to each item, we discussed how appropriate the question was in their opinion to describe their mental state throughout the hospitalization and whether they would change anything in the wording. At the end of this part of the discussion, the subjects were asked how many times a day they would be willing to report their mental

state, how many items they would be ready to answer, and what additional questions they would like to be asked to learn about their condition. In addition, we examined the patients' attitudes regarding their agreement to answer questions via mobile phone and their agreement to continue answering a similar questionnaire after their discharge from the hospital.

### **Research Process**

The focus groups were held at Sheba Medical Center on 5/18/22, 08/9/22, and 11/09/22. The groups were guided by the researcher and another facilitator, who work as senior clinical psychologists in the psychiatric inpatient wards at the Sheba Medical Center. A professional transcriber attended each group and typed the conversation throughout the focus groups. The transcripts of the discussions in the focus groups were qualitatively analyzed. After collecting and processing the data from the focus group, the ESM questionnaire was improved and refined, considering the findings.

2. **Running the monitoring model - Feasibility and Validity phase** - this phase will begin in the middle of 2023 and is expected to continue for 18 months.

### **Participants**

To conduct the monitoring model, we will recruit 100 subjects hospitalized in the inpatient wards. To receive feedback on implementing the monitoring model from the multi-disciplinary care team working in the wards, we will recruit 30 multi-disciplinary team members. The running will be carried out in two stages:

- Pre-Test - 20 patients and feedback from 5 multi-disciplinary – estimated time – 3 months.
- Field Test - 80 additional patients and feedback from 30 multi-disciplinary staff members – estimated 12 months.

The study inclusion criteria for the patients: adults are consenting hospitalized in a psychiatric hospital at the Sheba Medical Center in the open part of the ward who owns a mobile smartphone. Exclusion criteria: patients with a low level of treatment compliance, patients with a developmental or intellectual disability, complex organic conditions including dementia, patients who cannot read and write in the Hebrew language, and patients who are incapable of informed consent.

The study inclusion criteria for the multi-disciplinary team: multi-disciplinary team members who work in the psychiatric inpatient wards at the Sheba Medical Center. The staff members will have a valid Israeli license (from the professions of medicine, nursing, psychology, social work, and occupational therapy).

## **Indices**

### **Pre-test indices –**

1. The process involves selecting ESM questionnaire items based on their distribution indices to ensure optimal item distribution. It also includes refining the wording of items with low variability scores within and between subjects, aiming to enhance their variability.
2. We will evaluate the satisfaction indicators of the clinical staff working in the ward based on the monitoring indicators. If needed, we will enhance the implementation of the monitoring model within the clinical team in the ward.

### **Field test indices –**

3. The validation of the ESM questionnaire will be conducted by comparing the change trends in the questionnaire indices during a 14-day psychiatric hospitalization period to the change trends in four different measurements of psychiatric symptoms assessed by the PANSS diagnostic tool, which is widely recognized as the gold standard in psychiatric symptom assessment. The subject's assessment using PANSS will be conducted at four different time points:
  - a. T1 - at study entry (day 1)
  - b. T2 - during the first week of the study (between days 4-6)
  - c. T3 - during the second week of the study (between days 10-12)
  - d. T4 - at the end of the study (day 14)
4. Feasibility and compliance:
  - a. The responsiveness to participation in the monitoring model - The number of subjects who agreed to participate in the study out of the subjects we offered to participate.
  - b. The extent of responding to the self-report questionnaires over 14 days multiplied by three times a day.
  - c. The degree of responsiveness to wearing and charging the smartwatch for 14 days.

- d. The degree of difference between subjects with different psychiatric diagnoses (psychotic spectrum, depression, mania, and personality disorders) in their adherence and responsiveness to agree to participate in the study, answer the self-report ESM questionnaires and wear and charge the smartwatch.
- 5. The validity of the subject's ESM self-reports on sleep quality and activity level:
  - a. The validity of the subject's self-reports on sleep quality -The subject's self-reported data about his sleep quality and number of awakenings will be compared to physiological indicators that the smartwatch will collect (number of hours of sleep, number of awakenings) and will be equalized in addition to the medical reports of the nursing staff in the ward.
  - b. The validity of the subject's self-reports on his activity level:  
The subject's self-reported data about his energy and activity level will be compared to physiological indicators that the smartwatch will collect (number of steps, accelerations) and will be equalized in addition to the reports of the nursing staff in the ward.
  - c. The degree of difference between subjects with different psychiatric diagnoses (psychotic spectrum, depression, mania, and personality disorders) in correspondence between the self-report and the physiological indices and the reports of the nursing staff.
- 6. The effect of exposing the psychiatrists to the patient's monitoring indicators on their clinical decisions regarding him will be examined in a short questionnaire that the physician will fill out after each medication change and mark on a Likert scale of 1-5 - how much the exposure to the monitoring indicators influenced the clinical decision.
- 7. Patient satisfaction: After 14 days of monitoring, the subjects will report their satisfaction with using the monitoring model throughout the hospitalization through questionnaires.
- 8. The satisfaction of the multi-disciplinary teams: At the end of the study, the teams will report through questionnaires on their satisfaction with using this monitoring model and its influence on the team's clinical decision-making.

## **Research Process**

After recruiting the patient for the study and signing informed consent, the monitoring application (Datos Health) and the wearable smartwatch application (Garmin) will be installed on the patient's smartphone. The patient will receive an extensive explanation from the research team's representative on the self-reporting method and will experience using the application.

From this stage, the hospitalized subject will receive ongoing clinical care, alongside participation in monitoring indicators by self-reporting in the ESM questionnaires using the Datos Health application and physiological indices monitoring by using the Garmin smartwatch. The trial will end after 14 days or until the patient's discharge (whichever comes first). The ESM self-report sampling will be conducted a frequency of 3 times a day in a semi-random manner:

- The first sample will be randomly sampled between 8-10 am.
- A second sample will be randomly sampled between 1-3 pm.
- A third sample will be randomly sampled between 7-10 pm.

In each clinical discussion of the subject's mental state, the ward staff will watch the dashboard of the Datos Health application, which will display the subject's self-report measures and physiological indicators. For each change in the patient's clinical status, determined by the physician (change of medication, vacation, preparation for discharge, discharge), the physician will answer a questionnaire in which he will document how much (between 1-5) the clinical decision was influenced by the monitoring indicators he observed.

The feasibility and compliance, Validity, and changes in the patient's condition over timeline indicators will be collected for 14 days and analyzed at the study's end. The patient satisfaction indicators will be tested after 14 days of monitoring through a questionnaire sent to each subject. The satisfaction indicators of the clinical staff in the ward will be tested through questionnaires sent to the clinical staff at the end of the study.

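### The protocol neither masks the watch readings from patients nor records whether they looked at them, so the Aim 4 agreement between self-report and watch may be inflated, chiefly for number of awakenings

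*Protocol*

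**What the plan says.** Protocol, Research Process (second phase): once consent is signed, "the monitoring application (Datos Health) and the wearable smartwatch application (Garmin) will be installed on the patient's smartphone". Under Participants for that phase, eligible patients are those "in the open part of the ward who owns a mobile smartphone", so the phone is the patient's own and not a study device. The patient also wears and charges the watch for 14 days (Field test indices, item 4c).

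Specific Aims, aim 4, assesses the validity of self-reported sleep quality and activity by "comparing the self-report ESM data with the physiological indicators collected by the smartwatch". The field test indices give the pairs:

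- Item 5a, sleep: "The subject's self-reported data about his sleep quality and number of awakenings will be compared to physiological indicators that the smartwatch will collect", namely hours of sleep and number of awakenings.
- Item 5b, activity: "The subject's self-reported data about his energy and activity level will be compared to physiological indicators that the smartwatch will collect", namely steps and accelerations.
- Item 5c asks whether the correspondence differs by diagnosis.

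Aim 4 has a second comparator: "the ESM indices will be compared to reports from the nursing staff on the ward".

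On timing, "The first sample will be randomly sampled between 8-10 am", with further prompts at 1-3 pm and 7-10 pm. The only viewing of physiological data that the protocol describes is by staff: "the ward staff will watch the dashboard of the Datos Health application, which will display the subject's self-report measures and physiological indicators". Whether patients see their own watch values is neither stated nor excluded. The patient training described covers the self-reporting method and use of the application.

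**The concern.** A validity comparison needs the self-report to be formed without knowledge of the measurement it is checked against. Here the patient carries the source of that measurement on the wrist, and its app sits on the phone used to answer the prompts. The morning prompt ordinarily comes after the night has been recorded, and the afternoon and evening prompts come after part of the day's activity has been recorded.

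If a patient consults the reading first, agreement can mean either that patients report accurately or that they read the watch. The data as planned could not separate the two. Item 5c would inherit the problem if diagnostic groups differed in how often they looked, which is itself an assumption.

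This cannot be left to the analysis plan. Whether a patient looked is known only when the prompt is answered, and if it is not recorded then, no later analysis can recover it.

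**Working it through.** The protocol gives no agreement coefficient, target or sample-size derivation for Aim 4, so there is no figure to reproduce. The check has two parts.

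**1. Which items are exposed**

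| Self-reported | Watch value | Same quantity on both sides? |
|---|---|---|
| Number of awakenings | Number of awakenings | Yes |
| Sleep quality | Hours of sleep, awakenings | No, a rating against a measurement |
| Energy, activity level | Steps, accelerations | No, a rating against a measurement |

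Only awakenings could be copied directly. For the ratings, a reading could at most shift the answer. The initial questionnaire, before later refinement, had 15 five-level Likert items plus a 1-100 mood scale, so a step count or a number of hours could not simply be repeated on most of its items.

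**2. How large the effect could be (illustration; every input is an assumption)**

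Let W be the watch value and O the unaided report, both standardised, with true correlation r0. A share f of reports is anchored on the watch with weight w, giving S = (1 - w)·O + w·W. The remaining reports are S = O. Then

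- Cov(S, W) = r0 + f·w·(1 - r0)
- Var(S) = 1 - 2·f·w·(1 - w)·(1 - r0)
- observed correlation = Cov(S, W) / √Var(S)

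With w = 1 (full copying) this becomes f + (1 - f)·r0.

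For r0 = 0.30:

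- f = 10%, w = 0.25: 0.3175 / √0.97375 = 0.32
- f = 10%, w = 1: 0.10 + 0.90 × 0.30 = 0.37
- f = 25%, w = 0.25: 0.34375 / √0.934375 = 0.36
- f = 25%, w = 1: 0.25 + 0.75 × 0.30 = 0.475, or 0.48

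The range over other assumed values, from w = 0.25 to w = 1:

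| True r0 | f = 0 | f = 10% | f = 25% | f = 50% |
|---|---|---|---|---|
| 0.20 | 0.20 | 0.22-0.28 | 0.26-0.40 | 0.33-0.60 |
| 0.30 | 0.30 | 0.32-0.37 | 0.36-0.48 | 0.42-0.65 |
| 0.50 | 0.50 | 0.52-0.55 | 0.54-0.63 | 0.59-0.75 |

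A simulation of 1,000,000 draws gives the same values. With no anchoring there is no bias; with anchoring, the bias in this model is upward. The upper ends need exact copying on a common scale, so they are most relevant to awakenings.

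**The case against.** The strongest reply is that the protocol says only that the watch app is installed. It does not say that sleep or step values are shown to the patient, or that anyone looks at them, and raw accelerations may not be displayed at all. A reader might infer that patients can read the reference and that the agreement is therefore inflated. The documents do not support that; they support a possible bias of unknown size.

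A reader might also take the full-copying figures as the expected effect. They are the upper end of an illustration and fit poorly where a rating is set against a step count.

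Nor does Aim 4 rest on the watch alone. The nursing reports are not read from the patient's phone. They are not perfectly independent, since ward staff see the dashboard and a report anchored on the watch could shift that comparison too. But they are a second line of evidence. The primary objective, the comparison with the PANSS (aim 3), is not touched.

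Finally, watch-face and app settings might sit in a device manual, and hiding the readings would alter a monitoring model whose wear compliance and patient satisfaction are themselves outcomes.

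All of this narrows the point and argues against compulsory masking. It does not supply the missing record: nothing in the protocol would show whether a given self-report was made with or without sight of the watch data.

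**Conclusion.** The point holds as a modest, inexpensive improvement to a secondary aim. The protocol puts the reference device's app on the patient's own phone and neither masks the readings nor records whether patients consulted them. If the values are visible to the wearer, self-report-to-watch agreement under item 5 may be inflated, mainly for number of awakenings and less for the sleep-quality, energy and activity ratings.

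The size cannot be determined from the documents. It depends on the unaided correlation, the share of reports affected and how strongly they are anchored, none of which the protocol gives. At an assumed true correlation of 0.30, the upward shift is 0.02 to 0.07 with 10% of reports affected and 0.06 to 0.18 with 25%.

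**What to change.** In Research Process (second phase):

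- Add one yes/no question after the sleep and activity items: did you look at your watch or its app before answering? Placing it after those items limits its influence on the answers.
- At installation, tell patients to answer from their own experience and not from the device.

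In Field test indices, item 5, including 5c: report self-report-to-watch agreement with all reports, and again without those where the patient had looked. The second result should be read as a sensitivity analysis, because consulted and unconsulted reports may differ in other ways.

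Hiding the sleep and step displays during the 14 days is optional where the device allows it. It should be weighed against the possible effect on wear compliance and satisfaction.

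Cost: one short item per prompt, at most 14 × 3 = 42 answers per patient, and a sentence in the patient instructions. The question may itself draw some attention to the watch.

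### Participation ends at day 14 or earlier discharge, but the last PANSS (T4) is dated day 14 and no text moves it to an earlier discharge

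*Protocol*

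**What the plan says.** All references are to the protocol; no SAP is at hand.

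- **End of participation** (Research Process, second phase): "The trial will end after 14 days or until the patient's discharge (whichever comes first".
- **Eligibility** (Participants, second phase): no minimum or expected length of stay is required.
- **PANSS schedule** (Field test indices, item 3): T1 on day 1, T2 on days 4-6, T3 on days 10-12, and "T4 - at the end of the study (day 14".
- **Use of the ratings** (General purpose; Specific Aims, aim 3): the primary objective compares ESM and PANSS symptom trends over 14 days, and aim 3 bases this on four PANSS ratings.
- **Compliance** (Field test indices, items 4b and 4c): "The extent of responding to the self-report questionnaires over 14 days multiplied by three times a day" and "The degree of responsiveness to wearing and charging the smartwatch for 14 days". Item 4d compares diagnoses on how far they "answer the self-report ESM questionnaires and wear and charge the smartwatch".

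The protocol does not say what happens to T3 or T4 when a patient is discharged before the stated day.

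**The concern.** The stopping rule shows that the authors expect some stays shorter than 14 days, but the last rating carries a calendar day that those patients never reach. A rater who follows the schedule as written will not see an early leaver at exit. ESM reports then run to discharge while the PANSS record stops days before, so the two trends cover different periods.

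Two features make this worth settling in the protocol. First, visit timing is protocol content, and a rating not taken at discharge cannot be recovered by any missing-data method. Second, discharge is unlikely to be unrelated to how the patient is doing: Research Process itself lists it among the changes in clinical status that the physician decides. The unrated days would therefore tend to be the days leading up to that decision, which matter for a comparison of change.

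**Working it through.** The protocol gives no power, effect size or early-discharge rate, so there is no figure of its own to reproduce.

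**1. Ratings reachable as dated** (windows from Field test indices, item 3)

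| Discharge day | PANSS ratings at most |
|---|---|
| before day 4 | 1 |
| 4-9 | 2 |
| 10-13 | 3 |
| 14 | 4 |

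Only a patient who stays to day 14 can have the four ratings of aim 3.

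**2. ESM days without a comparator.** A patient leaving on day 9 has the last PANSS on days 4-6, so the last 9 − 6 = 3 to 9 − 4 = 5 days are uncovered. A patient leaving on day 13 has the last PANSS on days 10-12, so 1 to 3 days are uncovered.

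**3. One patient's PANSS slope.** Assume a linear trend, equal independent errors, T2 on day 5 and T3 on day 11. The slope SE is proportional to 1/√Sxx, where Sxx is the sum of squared deviations of the rating days from their mean.

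- Full schedule {1, 5, 11, 14}: Sxx = 102.75.
- Day-9 leaver, literal {1, 5}: Sxx = 8, SE ratio √(102.75/8) = 3.58.
- Day-9 leaver with exit PANSS {1, 5, 9}: Sxx = 32, SE ratio √(102.75/32) = 1.79.

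Over all permitted T2 and T3 days the ratios are 2.7-5.1 without the exit rating and 1.7-1.9 with it.

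**4. Pooled over the 80 field-test patients.** Assume a common slope and exits spread evenly over days 7-13.

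- Literal schedule: leavers on days 7-10 have {1, 5}, Sxx 8; leavers on days 11-13 have {1, 5, 11}, Sxx 50.67. Mean = (4×8 + 3×50.67)/7 = 26.29.
- With exit PANSS: Sxx for days 7 to 13 is 18.67, 24.67, 32, 40.67, 50.67, 80.75 and 91. Mean = 48.35.

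With a share p leaving early, the SE ratio to the full schedule is √(102.75 / [(1−p)×102.75 + p×mean Sxx]).

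| p (assumed) | Patients of 80 | SE ratio, literal | SE ratio, exit PANSS | SE reduction from exit PANSS |
|---|---|---|---|---|
| 10% | 8 | 1.039 | 1.028 | 1 − 1.028/1.039 ≈ 1% |
| 25% | 20 | 1.108 | 1.074 | 1 − 1.074/1.108 ≈ 3% |
| 50% | 40 | 1.262 | 1.166 | 1 − 1.166/1.262 ≈ 8% |

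Most of the precision loss comes from the short stay itself, which no wording can cure.

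**5. Compliance base, for scale only.** If item 4b were scored out of 14 × 3 = 42, a patient who answers everything until discharge at the end of day 7 could reach at most 21/42 = 50%. Scored over prompts scheduled while in the study, the same patient has 21/21 = 100%.

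**The case against.** The best defence is that T4 already means the patient's own last day. The other entries in its list (study entry, first week, second week) can only refer to the individual's participation, and Research Process says when that participation ends. On this reading day 14 is merely the nominal day. That is probably the intent. It does not remove the problem, because the bracket names a single day, nothing tells the rater to act at an earlier discharge, and different raters could follow the text differently.

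A reader might go further and take the phrase to mean the close of the whole study, because item 8 uses it that way: "At the end of the study, the teams will report through questionnaires on their satisfaction with using this monitoring model". That inference is weak. Item 8 concerns a staff questionnaire, and a patient's PANSS at whole-study close would make no sense within T4's own list.

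A reader might also infer that compliance will be scored against a fixed 42 prompts, so that the diagnosis comparison in item 4d is confounded by length of stay. The protocol does not establish this. Item 4b is no formula, aim 2 describes watch wear over the hospital stay, and Research Process ends the trial at discharge, so no prompt falls due afterwards. The denominator can be settled at analysis from time-stamped data.

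Nor does the patient satisfaction timing ("After 14 days of monitoring, the subjects will report their satisfaction") show that early leavers are left out, since Research Process sends that questionnaire to every subject.

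Finally, it is fair to object that the gain in precision is small and that slope SE is not itself the validation target, which is agreement between trends. Both points stand.

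**Conclusion.** The point holds for T4. The stopping rule and the dated last rating are not reconciled, and followed literally an early leaver has no exit PANSS for the primary trend comparison. The text is incomplete rather than plainly wrong in intent, but the lost rating is irrecoverable and the remedy is cheap, so it should be corrected.

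The size is modest: about 1%, 3% or 8% off the pooled slope SE at assumed early-discharge rates of 10%, 25% or 50%, under a common linear slope, independent equal errors and evenly spread exits. The 3.6-fold figure describes one day-9 leaver and should not be read as the effect on the study. The true early-discharge rate is not in the document, so the overall effect is unknown. The link between discharge and clinical state is a judgement, and any bias from it has not been quantified.

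The compliance items need only a clarification; no error in them is shown.

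**What to change.** Reconcile Field test indices, item 3, with the stopping rule in Research Process:

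1. State T4 as day 14, or discharge if earlier, with this exit PANSS replacing any later scheduled ratings.
2. Use the actual study day of each rating as time when comparing the ESM and PANSS trends.
3. As a secondary clarification, say that items 4b and 4c are taken over the days the patient is actually in the study, and that item 4d uses the same bases, so that length of stay is not mixed with compliance.

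**Cost.** No added patients and no more than the four PANSS ratings already planned for each. The change is not purely one of wording: the ward must notify the PANSS rater of a coming discharge, and no present step does this. Exit ratings will have to be arranged at short notice, and some will be missed.
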